8.2 Trial endpoints

- 1. Primary endpoints: Lesion size and clinical response described as reepithelialization. Lesion size refers to ulcer size only, here, and the rest of the protocol.
- 2. Secondary endpoint: safety and tolerance of WR 279,396.
- 3. Third end point: D0 to D10 Deep Lesion Dermis Parasite Load Reduction Ratio.

8.3 Study Population/Site

The study population will be selected from adults (≥ 18y) patients and children above 15y in Tunisia (Old World). Direct benefits to all subjects enrolled in the study are: a) elimination of bacterial infections by keeping the lesion clean; b) direct access to a medical team that will perform a medical history, physical exam, dermatology exam, and

laboratory tests; c) complete parasitological diagnosis, d) the possibility of cure without parenteral or intralesional antimony treatment

The recruitment process will be based on active case detection of patients with typical lesions in the primary health care centers and schools of the study area in Sidi Bouzid and Elmnara. Suspected cases based on clinical and epidemiological criteria will be identified by the diagnostic team composed of nurses trained by the study team in Tunisia. The central team will review all suspected cases, verify clinical inclusion criteria and perform a direct exam and culture for parasites as usually practiced in the primary health care system. Patients with positive lesions will be asked for written informed consent after the study is explained in accordance with the protocol requirements. Those who agree to be included in the study will continue the whole process of laboratory and other clinical inclusion/exclusion tests. After performing all the tests as described in the protocol, the principal investigator will review all the information for every case and make the inclusion decision according to the protocol and the protocol checklist.

8.4 Number and randomization of lesions

Fortyeight lesions (48) on fortyeight patients (48) will be studied. Efficacy will be evaluated in terms of the number of lesions cured i.e. percentage of subjects cured at D50 (D1 is the first day of treatment) with no relapse during 3 months post-treatment follow-up. Cure is defined as 100% reepitheliazation without relapse by 3 months. If a patient has more than 1 lesion, all lesions will be treated with WR 279,396, but the results of only 1 lesion (primary lesion) will be used for parasitological evaluation, and kinetic/clinical surrogate analysis. The lesion chosen will be the uppermost, primary ulcerative, parasitologicaly positive lesion on the body that is in a biopsy friendly area, or if two lesions are equally uppermost, the patient's left (located in the left half of the body) uppermost primary ulcerative lesion that is biopsy friendly. Biopsy friendly areas exclude the face, ears, fingers, toes and, in patients > 50 or with arterial or venous impairments, any area below the knees in patients older than 55 or with previous history of lower limbs venous or arterial insufficiency.

Patients will be enrolled in the study in the order they consent and given Subject's Numbers.

8.5 Inclusion criteria

- 1. Age: $\geq 15 \leq 75$ years old
- 2. Lesion character: each diameter (horizontal and vertical) of the lesion test must measure ≥ 7 mm, the lesion must be primarily ulcerative (i.e., not vertucous or nodular) and located in a biopsy friendly site of the body
- 3. Parasitological diagnosis: have cutaneous leishmaniasis proven parasitologically in lesion selected for inclusion in study (lesion test).
- 4. Informed consent: have given written informed consent to participate in the study: (i.e. patient or legal representative).

8.6 Procedures to evaluate inclusion/exclusion criteria

- 1. Medical history, with particular attention to skin, lymphatic system & mucosal membranes
- 2. Physical examination
- 3. Dermatological examination: including measurement of leishmaniasis lesions
- 4. Urinalysis
- 5. Complete blood count (WBC, platelets, Hgb)
- 6. Serum chemistries: creatinine, alanine aminotransferase (ALT) or aspartate aminotransferase (AST), glucose, Na, K.
- 7. Urine pregnancy test

8.7 Exclusion (Non-inclusion) criteria

- 1. Drug intolerance: history of known or suspected hypersensitivity or idiosyncratic reactions to aminoglycosides in the patient or immediate family members.
- 2. Previous use of antileishmanial drugs (within 2 months) or present use of routinely nephrotoxic or ototoxic drugs.
- 3. Potential for follow up: Have less than 4 months time remaining in present address and/or plans to leave the area for more than 30 days.
- 4. Extent of disease: More than 10 lesions or lesion ≥ 5 cm or a lesion less than 2 cm from eye, in the ear, or a lesion in the face, that in the opinion of the attending dermatologist could potentially cause significant disfigurement.
- 5. Location of disease: mucosal involvement.
- 6. Disseminated disease: clinically significant lymphadenitis with nodules that are painful and > 1 cm in size in the lymphatic drainage of the ulcer.
- 7. Concomitant medical problems: significant medical problems of the kidney or liver as determined by history and by the following laboratory studies:
 - Kidney: clinically significant abnormalities of urine analysis, serum levels of Creatinine, BUN, total proteins > upper limit of normal for the laboratory.
 - Liver: AST or ALT > upper limit of normal for the laboratory.
 - General: glucose, Na, K, > upper limit of normal or < lower limit of normal for the laboratory.
 - Volunteers in whom these normal laboratory values are exceeded by less than 25% will not be automatically excluded. These volunteers will be evaluated on the basis of history, physical, as well as laboratory values.
- 8. Scheduled or ongoing pregnancy as determined clinical and biological criteria.
- 9. Presence of signs or symptoms of peripheral neuropathy, myasthenia gravis or neuromuscular block

8.8 Duration of Study

Each patient will be treated for 20 days, and be followed for 3 further months. Enrollment will start in October 2005 and the study will end in March 2007.

8.9 Dosages and Administration of Drugs

Test articles to be used are:

Group 1: WR 279,396 (paromomycin sulfate 15%, gentamicin sulfate 0.5%, water to dissolve the aminoglycosides, AQIC base) and permanently covered with a polyurethane dressing (Tegaderm). i.e., polyurethane-covered perforated gauze fixed to skin through hypoallergenic medical tape.

Group 2: WR 279,396 (paromomycin sulfate 15%, gentamicin sulfate 0.5%, water to dissolve the aminoglycosides, AQIC base) without the polyurethane dressing i.e., gauze fixed to skin through hypoallergenic medical tape.

The method of administration of topical in 2 groups will be as per SOP.

The topical preparations were prepared by [name], University of Iowa, and distributed in 40-ml jars. The jars will be stored at 2–8°C at the Institut Pasteur in Tunis.

The method of administration of topical will be as per SOP. In brief, the lesion shall be appropriately disinfected. Then the formulation will be applied at a rate of about 0.0005 ml per 1 mm2 of lesion by covering uniformly the ulcer with a thin layer of ointment, onceaday for 20 days. Once a day shall mean that the administration occurs 24 hours after the first administration (+/- 4 hr). Medical personnel shall record that the formulation was administered. For Group 1 lesion/medication will be permanently covered with a polyurethane dressing (Tegaderm) and undisturbed (not wiped off, not wetted) for 4 hr after each application.

Iso-enzyme analysis of the parasite isolated from the lesion will be completed after treatment has been started. If the iso-enzyme analysis is L. aethiopica, the volunteer will be referred to his primary health care provider for the appropriate standard treatment (probably Glucantime). Should the volunteer elect to receive another treatment, the volunteer will be dropped from the study at the start of glucantime or other antileishmanial drug. Since no *L. aethiopica* has been reported in Tunisia in the last decade, the likelihood of a volunteer being dropped for this reason is remote.

8.10 Determination of adverse reactions

8.10.1 Determination of side effects

On each day on which topical is administered, patients will be observed/questioned for the occurrence of the following local side effects (i) on the edge of lesion (ii) on surrounding healthy skin (Please see Case Report Form):

-pain by history (none, mild, moderate, or severe)

-erythema (none, mild=barely perceptible, moderate=well defined,

severe=very red)

-edema (none, mild=barely perceptible, moderate=well defined,

severe=raised >2mm; life threatening = exfoliative)

-vertigo (mild, moderate, or severe) -tinnitus (mild, moderate, or severe)

-diminished hearing (mild, moderate, severe or profound)

Subjective evaluation

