6.5.3 Clinical toxicity of WR 279,396: Phase 1 study (33)

The aims of the phase I study were to investigate irritancy and phototoxicity due to WR 279396. In addition, blood was drawn to determine systemic toxicity (absorption of the aminoglycosides, alteration of kidney function and auditory function). In the irritancy study, 30 volunteers were administered WR 279,396, placebo cream (the AQIC base that contained urea), and white petrolatum to separate areas on the upper arm in a double-blinded manner for 15 days over a 20 day period.

The results of the irritancy study are:

- a) Active cream (WR 279,396): 12 volunteers had 1-4 erythematous papules for 1-6 of the 15 days of examined application; for 8 volunteers, the papules advanced to pustules; for 3 volunteers, the lesions evolved into erosions.
- b) Placebo cream (AQIC containing urea): 29 volunteers had fine wrinkling of the skin for 1-8 of the 15 days of application; 26 had +/- erythema (faint redness) for 3-10 days; 9 had 1+ erythema (erythema and edema of entire site) for 1-2 days. No patient had 2+ or 3+ erythema (vesicular changes or bullous changes).

One volunteer had acute dermatitis that developed at the sites both of active and placebo cream, that resolved. The volunteer was rechallenged with all ingredients in WR 279,396 known to cause allergic contact dermatitis, with negative results.

The interpretation of the irritancy study is that WR 279,396 can produce follicular irritant dermatitis with erythematous papules, and less frequently pustules and erosions. In addition, the urea in the AQIC vehicle, when it decomposes and is unbuffered by the aminoglycosides in WR 279396, characteristically produces mild irritancy.

In the phototoxicity study, 10 of the volunteers also received a challenge with ultra-violet light to areas of skin to which either WR 279,396 or the control substance, white petrolatum, was previously applied for 30 minutes. WR 279,396 was no different from the control substance in the degree of erythema produced.

In terms of systemic toxicity: examination of blood drawn on the last day of application or the following day, revealed that no volunteer had measurable blood levels (> 100 ng/ml) of paromomycin or of gentamicin. There was no statistical change in a kidney function test (creatinine). In audiometric tests pre-and post- topical application, more volunteers showed increases in high-frequency hearing than showed decreases in hearing.

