6.5.5 Summary of toxicity

The potential dermatological side effects of topical paromomycin consist of pruritus/ pain/ tenderness, erythema, edema, and vesicle formation. These side effects may result either from irritation or, particularly in persons previously sensitized to neomycin or gentamicin, allergic reactions.

Systemic side effects due to paromomycin and gentamicin are primarily due to kidney damage (increased BUN and creatinine) and 8th nerve damage (high-toned hearing loss, vertigo). At least for gentamicin, these systemic side effects generally occur when serum concentrations greater than that achieved with customary parenteral doses are administered. There are no studies in which the toxicity of paromomycin combined with gentamicin have been compared to the toxicity of the separate aminoglycosides. However, as mentioned above, in Colombia, WRAIR's formulation show no signs of systemic side effects and prove to be safe.

In the phase 1 study of dermatological irritancy and photoirritancy, WR 279396 caused slight follicular irritancy in 40% of volunteers when administered for 15 days over a 20-day period of time.

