Appendix A (Adverse or Unexpected Event Determination – Side Effects and Grades)

1. Cutaneous adverse reactions (i) on the edge of lesion (ii) on surrounding healthy skin [grade erythema separately from edema]

Grade 0: no reaction (no erythema or edema)

Grade 1: mild reaction (barely perceptible erythema or edema)

Grade 2: moderate reaction (well defined erythema or edema)

Grade 3: Severe reaction (very red erythema with raised > 2mm edema)

Grade 4: life threatening reaction (exfoliative dermatitis)

NOTE: Grade 3 reactions require immediate notification to Medical Monitor. Grade 4 reactions require immediate termination of treatment and ADVERSE EVENT NOTIFICATION.

2. Abnormal clinical laboratory values (DAIDS/NIH scale):

Parameter (units)	Grade 1	Grade 2	Grade 3	Grade 4
Creatinine (xULN)	>1-1.5	>1.5-3	>3-6	>6
AST/ALT (XULN)	1.25-2.5	>2.5-5	>5-10	>10
WBC (1,000/mm3)	1000-1500	750-999	500-749	< 500
PLT (1,000/mm3)	75-99	50-74	20-49	< 20
HGB (g/dL)	8-9.4	7-7.9	6.5-6.9	< 6.5

NOTE: Grade 2 require immediate notification to Medical Monitor.

Grade 3 and 4 reactions require immediate termination of treatment.

Grade 2, 3 and 4 laboratory values require evaluation of the volunteer. If the laboratory abnormality reflects clinically significant pathology, an ADVERSE EVENT report will be fill out and notification will occur.

3. Miscellaneous (associated with drug administration):

Pain:

Grade 0: none (feels no pain)

Grade 1: mild pain (does not interfere with daily activity)

Grade 2: moderate pain (interferes with daily activity)

Grade 3: severe pain (daily activities are interrupted)

NOTE: Grade 2 reactions require immediate notification to Medical Monitor. Grade 3 reactions require immediate termination of treatment and ADVERSE EVENT NOTIFICATION.

Vertigo:

Grade 0: none (feels no vertigo)

Grade 1: mild vertigo (does not interfere with daily activities)

Grade 2: moderate vertigo (interferes with daily activity)

Grade 3: severe vertigo (daily activities are interrupted)

NOTE: Grade 2 reactions require immediate notification to Medical Monitor. Grade 3 reactions require immediate termination of treatment and ADVERSE EVENT NOTIFICATION.

Tinnitus:

Grade 0: none (feels no ringing/buzzing/roaring etc.)

Grade 1: mild tinnitus (does not interfere with daily activities)

Grade 2: moderate tinnitus (interferes with daily activities)

Grade 3: severe tinnitus (daily activities are interrupted)

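### The tolerance assessment shown neither prompts for nor separately grades papules, pustules, erosions, pruritus or vesicles, so these may be under-ascertained or under-graded when the arms are compared

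*Protocol*

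**What the plan says.** **What is collected.** Protocol 8.10.1 states that on each day of application "patients will be observed/questioned for the occurrence of the following local side effects", at the lesion edge and on the surrounding healthy skin. The local items that follow are pain, erythema and edema; vertigo, tinnitus and diminished hearing are also listed. The section refers to the Case Report Form and ends with a subjective-evaluation line that has no stated content.

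**How it is graded.** Section 17.3 sends the reader to Appendix A for study-specific side effects and grades. Item 1 starts at "Grade 0: no reaction (no erythema or edema") and defines Grades 1 to 3 by the intensity of those two signs. Grade 4 is exfoliative dermatitis. Pain has its own scale in item 3.

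**What is already reported.** Section 6.5.3 concludes that "WR 279,396 can produce follicular irritant dermatitis with erythematous papules, and less frequently pustules and erosions". Section 6.5.5 adds: "The potential dermatological side effects of topical paromomycin consist of pruritus/ pain/ tenderness, erythema, edema, and vesicle formation".

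**How it will be used.** Section 8.2 makes safety and tolerance the secondary endpoint, and 9.2 plans a comparison of the two groups. Section 2.0 says that an efficacy gain must be large enough to justify the poorer tolerance and higher cost of the dressing.

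**The concern.** The skin reactions that the protocol attributes to this product in Phase 1 are not those that staff are told to look for each day. If they occur, two things can go wrong. Whether they are recorded may depend on someone noticing and volunteering them, in a trial that 8.12 says cannot be blinded. And once recorded, the cutaneous scale has no step that tells a pustule or an erosion from plain redness.

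The stake is the tolerance side of the decision on occlusion. Section 2.0 promises extensive objective and subjective local tolerance data, and the choice of dressing for Phase 3 is meant to draw on it.

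**Working it through.** **Inputs.** The irritancy study in 6.5.3 had 30 volunteers ("30 volunteers were administered WR 279,396, placebo cream" and white petrolatum, at separate sites on the upper arm). For the active cream, "12 volunteers had 1-4 erythematous papules for 1-6 of the 15 days of examined application; for 8 volunteers, the papules advanced to pustules", and "for 3 volunteers, the lesions evolved into erosions".

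**Step 1: reproduce the protocol's figure.** Papules: 12/30 = 40.0%, which matches the 40% follicular irritancy stated in 6.5.5.

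**Step 2: the other two rates.** Pustules: 8/30 = 26.7%. Erosions: 3/30 = 10.0%. The counts describe successive stages of the same reaction, so they are nested and must not be added.

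**Step 3: set the sections side by side.**

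| Reaction | Where the protocol reports it | Prompted in 8.10.1 | Own grade in Appendix A |
|---|---|---|---|
| Pain | 6.5.5; earlier Phase 2 studies | Yes | Yes (item 3) |
| Erythema, edema | 6.5.5; A-9768.1 | Yes | Yes (item 1) |
| Papules | 6.5.3, WR 279,396, 12/30 | No | No |
| Pustules | 6.5.3, WR 279,396, 8/30 | No | No |
| Erosions | 6.5.3, WR 279,396, 3/30 | No | No |
| Vesicles | 6.5.5, potential effect; patient reports in 6.5.2.1 from another formulation | No | No |
| Pruritus | 6.5.5, potential effect; patient reports in 6.5.2.1 from other formulations | No | No |

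**Step 4: run cases through Appendix A item 1.**

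- A papule with barely perceptible redness is Grade 1. If it becomes a pustule and then an erosion while the redness stays the same, it is still Grade 1.
- Pruritus with no redness or swelling is Grade 0.

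By contrast, the Phase 1 reading described in 6.5.3 tied its upper erythema grades to vesicular or bullous change. Appendix A has no such step.

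**Step 5: can the loss be sized?** No. That would need the share of these events that goes unrecorded without a prompt, and whether the share differs by arm. The protocol gives neither figure.

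**The case against.** The case on the other side has considerable force.

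- **General capture exists.** Section 17.2.1 requires every adverse event, whether seen by staff or reported by the patient, to be documented at each visit. A pustule noticed at the daily examination belongs in the record. A reader might infer that the trial will miss these reactions; the protocol does not support that. What stands is the lack of a prompt and of a specific grade.
- **The form is not shown.** The CRF and the subjective-evaluation item may hold more. Appendix A, however, is shown in full on this point and lacks the grades whatever the CRF contains.
- **Most of these signs would not score zero.** The Phase 1 papules were erythematous, and the vesicles in 6.5.2.1 came with erythema, so at least some redness would be graded. Only isolated pruritus clearly falls to Grade 0. What is lost for the others is form and progression.
- **Two of the five are not reported for WR 279,396.** The patient reports of pruritus and vesicles concern other paromomycin formulations. The vesicles came with one that also contained methylbenzethonium chloride, which 6.5.2.1 suspects as a cause, although it also notes pruritus with paromomycin in paraffin alone.
- **The closest precedent is reassuring.** A-9768.1, with this drug under occlusion twice daily, found local reactions in 11 of 49 treated patients (22.4%), described only as mild pain, redness and edema. Colombia, without occlusion, reported only grade 1 pain. This lowers the expected frequency. It does not show absence, because the protocol does not say whether the other signs were solicited there.

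A reader might also multiply the Phase 1 rates by the arm size to forecast papules, pustules and erosions per arm. That is not supported: the rates come from intact skin in volunteers, and a 40% papule rate sits badly beside 22.4% for all local reactions in patients.

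Finally, both arms use the same instrument and no differential error is shown. Unblinded assessment affects the prompted items too, so prompting reduces reliance on volunteered reports but does not remove that bias.

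**Conclusion.** The point holds as a measurement gap. In the text shown, five skin reactions that the protocol names are neither solicited daily nor separately graded. Three of them (papules, pustules, erosions) were observed with WR 279,396 itself, at nested Phase 1 rates of 40.0%, 26.7% and 10.0%, and they are enough to carry the finding.

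Under-ascertainment is possible, and under-grading follows directly from the wording of the scale. Neither the size nor the direction of any effect on the comparison between arms can be derived. The severity is minor to moderate: the gap concerns the secondary endpoint and leaves the efficacy analysis untouched. The conclusion assumes that the CRF does not already list these items; if it does, only the Appendix A part remains.

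**What to change.** Add two prompted items to the 8.10.1 daily checklist and to the CRF, if not already there, at the same two sites (lesion edge and surrounding skin):

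1. pruritus: none, mild, moderate or severe;
2. papules, vesicles, pustules or erosions: absent or present, with the type.

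Include both, by patient, in the tolerance comparison under 9.2.

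Reconcile Appendix A item 1 with 6.5.3 and 6.5.5 so that these signs are not recorded as no reaction. Appendix A attaches notification and termination notes to its grades, so this change should be limited to recording. Whether any of these signs should trigger notification or the stopping of treatment is for the sponsor and its clinicians to set.

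The cost is slightly more recording at an examination already done on each of the 20 treatment days, with no new visit or procedure.

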2.0 BACKGROUND

An analysis of the data from the recent WR 279,396 study (HSRRB Log # A-9768.1) indicates that by day 50, cure rate was 91.8% in the treatment group and 73.2% in controls ($x^2 = 5.60$, p= 0.017) and complete cure response was 95.8% among the former versus 75% among the latter ($x^2 = 8.04$, p= 0.004). The global healing rate is already much higher than the previous (placebo) 25% healing rate in the same area using the same evaluation criteria (Ben [name] 95). The occlusive dressing used during the ongoing trial may have positively influenced the healing rate, by enhancing drug diffusion into the deep dermis and accelerating the reepithelialization process. The practicability of polyurethane adhesive dressings was not perfect however. Local reactions (mild pain, redness and edema) was noticed among 22 patients (11 among the treatment group (22.4%) and 11 among controls (28.6%), NS. Although no patient stopped drug applications, topical treatment might be improved by simplifying the regimen. WR 279,396 without occlusion was superior to placebo in a Colombian Phase 2 study (Soto 02) making it the reference schedule. No tolerance problems were observed in this trial.

The Office of the Surgeon General, United Sates Army represented by USAMMDA holds the IND for WR 279,396 and will continue the development of the product through a commercial pharmaceutical partner in order to obtain licensure by the FDA.

Thus, this Phase 2 study is to determine whether WR 279,396 with occlusion (a polyurethane dressing) is more effective than WR 279,396 without occlusion. Furthermore, a consistent difference in efficacy will be necessary to justify the relatively lower tolerance and higher cost of an occlusive dressing, and this study will help determine which form of dressing should be used.

Extensive objective and subjective local tolerance data will also be captured during this trial, as well as surrogate markers (parasite loads and aminoglycosides concentration in the deep dermis) that may help to determine the optimal number and duration of treatments. Finally, this study, which will be conducted from October 2005 through March 2007, will bridge the time gap between the 2004 Phase 2 study and the planned 2006 Phase 3 study. This will serve to keep the clinical team in Tunisia active and ready to start the next trial should that study be necessary.

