6.0 BACKGROUND OF LEISHMANIASIS

6.1 Natural history and drug treatment of Old World cutaneous leishmaniasis

6.1.1 Old World cutaneous leishmaniasis

Cutaneous leishmaniasis typically presents as a papule that enlarges over approximately 1 month into an ulcer with raised edges and a necrotic center (1). The mean area per ulcer in one study was 400 mm2 (2). Nevertheless, rare ulcers are 2,000 mm², and a rare patient may have 20 ulcers. The spontaneous cure rate over 6-8 weeks for cutaneous leishmaniasis caused by members of the L. major or L. tropica complex in the Old World ranges from 15-45% (3,4). The most reliable figures come from L. major disease in Tunisia and Iran, for which rates of 20-44% are reported (3,4). Although frequently follow-up in such studies is performed for 1 year, in a recent study of 27 relapsed lesions (5), only 2 occurred between 6 and 12 months after the end of therapy, and follow up for 6 months therefore seems sufficient.

Standard treatment is with intralesional injections of pentavalent antimonials. When 1-3 ml of Glucantime were administered intradermally once a week for 5 consecutive weeks to 20 patients with L. tropica in Syria, a cure rate of 76% was achieved (6). This regimen of Glucantime is considered successful in most L. tropica or L. major endemic areas, although these results are substantiated by only one controlled study. However, the regimen requires at least five painful intradermal injections which can hardly be performed in children and/or when lesions are located near eyes, mouth or nose. The overall cost of one intradermal injection is about \$30 in France; \$150 for a complete treatment course. For multiple and/or periorificial lesions that can't be injected, standard treatment is with pentavalent antimonials intramuscular at a dosage of 10-20 mg antimony (Sb)/kg/day for

10-20 days. This regimen of Pentostam or Glucantime is successful in Central and South America with a ~90% cure rate with 1 year follow up. A lower cure rate (50%) of cutaneous leishmaniasis was achieved in Algeria in a L. major endemic area (7). The regimen requires 20 days of injections for an outpatient dermatological disease, is expensive (~US\$200 per course), and is potentially or frankly toxic to the heart, liver, pancreas, hematopoietic system, and musculoskeletal system (8).

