8.17 Procedural timetable

	Procedure	Therapy Period (days)	Follow-up (#Days)
--	-----------	-----------------------	-------------------

	0/1	10	20	50±7	90±7
Informed Consent	X				
Demographic Details	X				
Medical History	X				
History of Leishmaniasis	X				
Physical Exam	X				
Dermatology Exam	X				
Hearing Test	X	X	X		
Romberg Test	X	X	X		
CBC (WBC,platelets, Hgb)	X				
AST or ALT	X				
Serum Creatinine	X	X	X		
Glucose, Na, K	X				
Pregnancy Test	X				
Urinalysis	X		X		
Measure ulcer and induration	X	X	X	X	X
Clinical Evaluation of Lesion	X	X	X	X	X
Photograph Lesion	X	X	X	X	X
Parasitologic Tests	X				
Cutaneous Biopsy	X	X			
Aminoglycoside concentration	X	X			
Parasite load	X	X			
Leishmania Culture (Microdilution	X	X			
Test)					
Parasite load by DNA and RNA	X	X			
techniques					
Entrance Exam and Lab Test	X				
Check List					

Drug Therapy	Days 1 through 20
Local Toxicity	Days 1 through 20

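### Erythema and edema at the lesion edge are graded on absolute scales with no named pre-treatment grade, so disease signs can count as reactions and dilute the edge-site tolerance comparison

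*Protocol*

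**What the plan says.** **Role of tolerance.** Section 8.2 makes safety and tolerance the secondary endpoint, and section 9.2 has a statistician compare it between the two groups. Section 2.0 makes it part of the decision on occlusion: "a consistent difference in efficacy will be necessary to justify the relatively lower tolerance and higher cost of an occlusive dressing".

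**Scoring.** The timing in section 8.10.1 is "On each day on which topical is administered", when "patients will be observed/questioned for the occurrence of the following local side effects (i) on the edge of lesion". There are two sites: "local side effects (i) on the edge of lesion (ii) on surrounding healthy skin (Please see Case Report Form". Each sign runs from none through mild (just visible) and moderate to severe. The top edema categories are "severe=raised >2mm; life threatening = exfoliative". Appendix A item 1 repeats these grades, under a heading on adverse cutaneous reactions, and calls every grade from 1 upward a reaction.

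**Schedule.** In section 8.17 the local toxicity row reads "Days 1 through 20". Sections 8.10.1, 8.17 and 9.2 and Appendix A name no grade before the first application and no rule that only worsening counts.

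**The untreated lesion.** Section 6.1.1 describes it as "an ulcer with raised edges and a necrotic center", and section 8.5 requires the test lesion to be mainly ulcerative.

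**The concern.** The first scoring site is the part of the lesion that the protocol itself describes as raised by the disease, and the severe edema category is defined by height. Without a reference grade, an assessor or analyst cannot tell from the record whether a graded sign was there before treatment or arose from the cream or dressing.

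Randomisation balances such signs between arms in expectation, so they do not favour either arm. They do raise the recorded edge rate in both arms and pull the two rates together. Tolerance is one side of the balance that the trial is meant to inform, so a diluted edge comparison weakens that side.

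The gap also has to be closed before enrolment. An SAP, if one exists, can choose how to count reactions, but it cannot supply a pre-treatment grade that nobody recorded.

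**Working it through.** **1. Is there a tolerance figure to reproduce?** No. The protocol gives no expected reaction rate, sample size or power for tolerance. Section 9.1 concerns cure only and is not touched by this point.

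**2. What is recorded at Day 0/1 (sections 8.12 and 8.17)?**

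| Measure | Day 0/1 value | Later values |
|---|---|---|
| Hearing, Romberg, creatinine | yes | Days 10, 20 |
| Ulcer and induration measurement, clinical evaluation of the lesion, photograph | yes | Days 10, 20, 50, 90 |
| Dermatology exam | yes | none listed |
| Local erythema, edema and pain grade | none named before application | Days 1 to 20 |

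The other repeated safety measures have a starting value. The local grades have none that is named.

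**3. Effect on the edge comparison.** Let p be the true probability of a treatment-related edge reaction in an arm. Let q be the share of edges that would score from disease alone. Assume that q is the same in both arms (randomisation) and that disease signs and reactions are independent within a patient. Then:

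- recorded rate = 1 - (1-q)(1-p) = p + (1-p)q
- recorded difference = (1-q)(p_A - p_B)

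The shrinkage factor (1-q) does not depend on the reaction rates. As an illustration with assumed true rates of 40% and 10%, which are not in the documents:

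| q | Recorded rates | Recorded difference | Share kept |
|---|---|---|---|
| 0 | 40% v 10% | 30 points | 100% |
| 0.25 | 55% v 32.5% | 22.5 points | 75% |
| 0.50 | 70% v 55% | 15 points | 50% |
| 0.75 | 85% v 77.5% | 7.5 points | 25% |

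The difference disappears only at q = 1.

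**4. What do the documents say about q?** They do not give it. The nearest evidence is the earlier Old World trial (section 6.5.4.2), in which 22 of 90 patients had local reactions: 22/90 = 24.4%. The recorded rate p + (1-p)q is never below q. So, if scoring there was similar, q was at most about 0.24 and at least 1 - 0.244 = 75.6% of the difference would survive. Those reactions lasted 1 to 3 days, whereas a standing disease sign would be recorded for longer, which points to a still lower q. That trial's scale is not stated, so this is an indication and not a bound for the present trial.

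**5. Can a loss of power be stated?** No. It needs q and both true edge rates. The occluded active arm of the earlier trial had 11/49 = 22.4% with local reactions, but under twice-daily treatment. The Colombian trial without occlusion (section 6.5.4.1) reports only pain, also under twice-daily treatment. No rate for either once-daily arm is given.

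**The case against.** **The healthy-skin score carries the dressing contrast.** Both signs are graded separately on surrounding skin, and the protocol's dressing-specific worry is removal of the Tegaderm (sections 4.0 and 7.0), which that site can capture. This stands. A reader might infer that the tolerance difference is hidden altogether. The text does not support that: the dilution is partial, equal in expectation in both arms, and confined to one of two sites. But the protocol does not rest the comparison on healthy skin alone, so the edge score still needs a reference.

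**Assessors may not score disease as reaction.** Section 8.10.1 asks for side effects, Appendix A grades reactions, and the investigator determines causality (section 17.2.3). A raised border need not be edema, and induration is measured separately. This stands as a reason why q may be small. It leaves the separation to daily judgement without a recorded starting grade. Section 6.1.1 mentions raised edges only, giving neither redness nor a height, so it does not follow that a typical untreated ulcer would score severe.

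**A baseline may exist.** The Case Report Form is not shown and could hold one. Section 8.10.1 does not say whether the Day 1 score comes before or after application. Photographs and the lesion evaluation would allow partial reconstruction. All true, but none of these is a named erythema or edema grade, and the protocol should settle the matter.

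**Counting rules belong in the SAP.** This is fair for the choice between worsening and absolute grades. It does not cover collection of the baseline.

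**Conclusion.** The point holds in a limited form. The protocol grades erythema and edema at the lesion edge by absolute appearance and names no grade before the first application, while describing the untreated edge as raised. Disease signs can therefore enter the record as reactions in both arms, and the edge-site difference shrinks to (1-q) of its true size. This assumes that disease signs are independent of arm and of reaction. The size of q is unknown. The earlier Old World trial suggests at most about 0.24 if scoring was alike, which would leave at least about three quarters of the difference.

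Two stronger readings should be resisted. A large loss of power might be inferred by assuming high values of q, but neither such values nor the reaction rates needed are supported by the documents. It might also be inferred that faster healing in one arm would look like improving tolerance, but the protocol specifies no analysis of scores over time that would produce this.

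The change is worth making because it is cheap, concerns a secondary endpoint compared between arms, and cannot be fully repaired after treatment has begun.

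**What to change.** - **Sections 8.10.1 and 8.17:** record the erythema, edema and pain grades at both sites at Day 0/1 before the first application. If the Day 1 score is already meant to be taken before application, say so.
- **Section 9.2:** compare the arms on worsening above the patient's own pre-treatment grade at each site. Report lesion edge and healthy skin separately, with absolute grades alongside.
- **Appendix A:** leave the notification and termination rules as they are, since they act on absolute grades and this point does not concern them.

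**Cost:** one extra form entry at a visit where the lesion is already examined, measured and photographed, plus a few lines of analysis wording. No new procedure or visit is needed.
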